6.1.3.2. Laboratory tests

General Biochemistry:	Sodium, potassium, chloride, glucose (random),
	blood urea nitrogen (BUN), creatinine, bilirubin
	total, alkaline phosphatase, AST, ALT, albumin,
	calcium, carbon dioxide, inorganic phosphate,
	magnesium, total protein and uric acid

Hematology: White cell count with differential (absolute values of neutrophil, lymphocyte, monocyte, eosinophil, and

basophil), red cell count, hemoglobin, hematocrit, MCV, and platelets count

Urinalysis: Color, clarity, specific gravity, pH, leukocyte, protein, glucose, ketones, bilirubin, blood, nitrite, urobilinogen. Microscopic examination will only be performed if dipstick test is outside the reference range for leukocyte, blood, nitrite or protein

Additional laboratory tests may be also performed by the medical laboratory as part of larger standard tests panels although not required for the subject's safety. All test results will be assessed by physician for clinical significance. Only test results required by the protocol and/or abnormal results will be entered in the clinical database and reported in the Clinical Study Report, based on the report requirement.

6.1.3.3. Other laboratory tests

A pregnancy test will be performed on female subjects at the end of the study.

6.1.3.4. Other tests

No other tests will be performed at the end of the study.

6.2. SAMPLING DURING THE STUDY

6.2.1. Blood sampling

In order to better understand and control for the presence of chlorhexidine in the environment, baseline levels will be assessed in each study period.

For baseline assessment, 3 blood draws will be performed prior to each treatment. A total of 12 blood samples will be collected (one tube of 6 mL each) in each study period. Samples will be collected into labeled tubes containing the appropriate anticoagulant as specified by the bioanalytical facility.

The complete schedule for each study period is presented in Table 2. The time of blood sample collection will be calculated according to the drug application schedule. The clock time of all blood draws will be recorded and reported for all subjects. For postdose samples, all deviations from the scheduled sampling time of 2 minutes or more will be reported in the final report.

The total volume of blood withdrawn, including ~ 20 mL required for screening, pre-dose and poststudy tests, should be approximately 236 mL per subjects. The total blood donation may be higher if repeat blood samples are required for safety assessments.

6.2.2. Urine sampling

No urine samples will be collected during the course of this study, other than for screening prior to each drug administration, as well as for safety reasons at the end of the study.

6.2.3. Sample processing, storage and shipping

Blood samples will be processed, split, stored, and shipped according to the sample processing instructions supplied by the bioanalytical facility.

6.3. SAFETY MONITORING

6.3.1. Vital signs

Blood pressure, pulse rate, respiratory rate and body temperature will be recorded within 120 minutes prior to each treatment, and at approximately 12 and 24 hours after each treatment. Vital signs will be monitored subsequently, if judged necessary by the medical investigator or designee.

6.3.2. ECG records

ECG will be recorded if judged necessary by the physician in charge.

6.3.3. Visual skin evaluation

Visual skin evaluation of the application site will be performed by the physician in charge or designee as follows:

Application site verification (for redness, markings, scars, etc.) will be documented prior to and approximately 4, 8 and 24 hours after each treatment.

6.3.4. Other measurements

General biochemistry tests will be performed before each period of the study.

7. ADVERSE EVENTS

7.1. **DEFINITIONS**

An adverse event (AE) is defined as any untoward medical occurrence in a subject administered an investigational product and which does not necessarily have a causal relationship with the treatment. An AE can therefore be any unfavorable and unintended sign (including a clinically significant abnormal laboratory finding, for example), symptom, or disease temporally associated with the use of an investigational product, whether or not related to the investigational product.

A suspected adverse reaction (SAR) is any adverse event for which there is a reasonable possibility that the drug caused the adverse event. 'Reasonable possibility' means there is evidence to suggest a causal relationship between the drug and the adverse event. A suspected adverse reaction implies a lesser degree of certainty about causality than adverse reaction, which means any adverse event caused by a drug.

An adverse event may be:

- A new illness
- Worsening of a concomitant illness
- An effect of the study medication including comparator; it could be an abnormal laboratory value as well as a significant shift from baseline within normal range which the Medical Investigator considers to be clinically important

Abnormalities in laboratory tests, in the measurements of vital signs, in visual skin evaluation or in other measurements performed after drug application or at the end of the study are to be recorded as adverse events only if they are medically relevant: symptomatic, requiring corrective treatment, leading to study discontinuation and/or fulfilling a seriousness criterion. If asymptomatic, but with a suspected underlying process, the Medical Investigator may consider the abnormalities to be medically relevant.

Surgical procedures themselves are not adverse events. They are therapeutic measures for conditions that required surgery. The condition for which the surgery is required is an adverse event, if it occurs or is detected during the study period. Planned surgical measures permitted by the clinical study protocol and the conditions(s) leading to these measures are not adverse events, if the condition(s) was (were) known before the start of study treatment. In the latter case, the condition should be reported as medical history.

A serious adverse event (SAE) or reaction is any untoward medical occurrence that at any dose:

• Results in death

- Is life-threatening
- Requires in-patient hospitalization or prolongation of existing hospitalization
- Results in persistent or significant disability or incapacity (defined as a substantial disruption of a person's ability to conduct normal life functions)
- Is a congenital anomaly or birth defect
- Is an important medical event that may jeopardize the subject or may require intervention to prevent one of the other outcomes listed above (according to medical judgment of the Medical Investigator)

7.2. SEVERITY ASSESSMENT

All adverse events will be graded as mild, moderate, or severe according to the following definitions:

- Mild: Causing no limitation of usual activities; the subject may experience slight discomfort.
- Moderate: Causing some limitation of usual activities; the subject may experience annoying discomfort.
- Severe: Causing inability to carry out usual activities; the subject may experience intolerable discomfort or pain.

Every effort will be made to obtain an adequate evaluation of the severity.

7.3. CAUSALITY ASSESSMENT

The Medical Investigator will determine the relationship of any adverse event to the Investigation Product according to the following criteria:

TERM	DEFINITION	
Reasonable Possibility	A temporal relationship exists between the AE onset and administration of the investigational product that cannot be readily explained by the subject's clinical state or concomitant therapies.	
	Furthermore, the AE appears with some degree of certainty to be related, based on the known therapeutic and pharmacologic actions or adverse event profile of the investigational product.	
	In case of cessation or reduction of the dose the AE may abate or resolve and it may reappear upon rechallenge.	
No Reasonable Possibility	Evidence exists that the adverse event has an etiology other than the investigational product.	
	For SAEs, an alternative causality must be provided (eg, pre-existing condition, underlying disease, intercurrent illness, or concomitant medication).	

7.4. DOCUMENTATION AND REPORTING OF ADVERSE EVENTS

For the purposes of this study, the period of observation of adverse events extends from the pre-trial evaluation until the end of the study. From screening to the first dose of the study, they will be recorded as screening events or as part of the medical history, as applicable. When AEs occur after initiation of study medication, they will be indicated as treatment-emergent AEs in the clinical study report. During the study, all adverse events spontaneously reported by the subject, observed by the clinical staff or elicited by general questioning will be recorded for all subjects and reported in the CRF.

If necessary, every effort will be made to obtain an adequate follow-up of the subjects. Should any subject choose to withdraw early from the study, they will be advised of the safety precautions to be taken.

Subjects will be questioned on their health status at the beginning of each study period and before each departure from the clinical site. Open-ended questions will be asked.

Classification will be performed by System Organ Class (SOC) and Preferred Term (PT) using the Medical Dictionary for Regulatory Activities (MedDRA), version 19.0 or higher.

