5. SELECTION OF STUDY POPULATION

5.1. NUMBER OF SUBJECTS

Twelve (12) subjects will be selected for inclusion in the study. A subject who withdraws subsequent to the pre-trial evaluations but before the application of the investigational product will not be considered as a drop-out and will not be included in the database. Standbys should be recruited and be available to replace a subject who withdraws prior to the first drug application. Drop-outs will not be replaced. Justification for the number of subjects is presented in section 9.4.

An effort will be made to include similar proportions of males and females in the study.

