6.1.2.1. Drug administration procedure

ReadyPrep[®] CHG Application (Treatment-1 and Treatment-2):

In two Treatment-1 and -2, a single topical application of ReadyPrep[®] CHG will be done on either the abdomen (surface area of approximately 5 x 5 inches) or the groin (surface area of approximately 5 x 2 inches) according to the randomization scheme.

The drug will be applied to a clean, dry, non-irritated, normal skin area. Possible hairs will be removed by means of scissors (no shaving) on the morning of dosing.

Approximately 30 minutes prior to any application, the site should be gently washed with room temperature water and dried without rubbing or heavy pressure with a gauze or similar cotton soft material. The application site must be allowed to dry for at least 15 minutes before drug application. After drying, the application site will be marked for dose location.

The topical application of ReadyPrep[®] CHG will consist of a 3-minute vigorous rub followed by a 1 minute dry time at the application site. The

1-minute dry time will be air drying without dabbing or rubbing. The time of dosing will be defined as the start time of the drug application on the skin.

Control Treatment (Treatment-3):

In Treatment-3, the same procedures as Treatment-1 and -2 will be performed, but without the topical application of ReadyPrep® CHG or placebo (no placebo ReadyPrep[®] cloth will be provided or used). Therefore, approximately 30 minutes prior, the site should be gently washed with room temperature water and dried without rubbing or heavy pressure with a gauze or similar cotton soft material. The application site must be allowed to dry for at least 15 minutes and after drying, the skin site will be marked. Subjects should be placed in the same position, for the same length of time, in the same area as they would be dosed.

The physician will remain at the clinical site for at least the first 4 hours following each treatment and will remain available at all times during the entire period of the study.

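### The database, CRF and treatment-emergent AE rules start at product application or first dose, but the analysis populations start at any treatment; Sequence 3 takes the no-application control first (minor)

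*Protocol*

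**What the plan says.** Two starting points are in use.

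**Start at the product or the dose**
- Section 7.4, before the start: "From screening to the first dose of the study, they will be recorded as screening events or as part of the medical history". After it: "When AEs occur after initiation of study medication, they will be indicated as treatment-emergent AEs in the clinical study report".
- Section 5.1, on a subject who passes screening and then leaves: "before the application of the investigational product will not be considered as a drop-out and will not be included in the database".
- Section 10.6 requires CRF data for each included subject and explains inclusion as having received an Investigational Product treatment.

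**Start at any treatment**
- Section 8.2 puts in the safety population everyone who received one or more of the study treatments.
- Section 9.1 uses the same threshold for the PK analysis, and adds that enough blood samples must have been taken.

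Section 4 lists the no-application control as Treatment-3 and gives it to Sequence 3 (n = 4) in Period 1. Section 6.1.2.1 says that in this period "the same procedures as Treatment-1 and -2 will be performed, but without the topical application of" the product, and that no placebo cloth is used. The same section fixes dosing by product contact: "The time of dosing will be defined as the start time of the drug application on the skin".

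**The concern.** For Sequences 1 and 2 the first treatment is a product application, so the two starting points coincide. For Sequence 3 they are separated by the whole control period and the wash-out that follows, Day 1 to Day 8 in Table 1. Two things are at stake.

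1. **The AE label.** The same event after the same control procedure could be a screening event in one sequence and treatment-emergent in another. The control is the reference against which tolerability of the two applications will naturally be read, and it is the only condition affected.
2. **Subject accounting.** A Sequence 3 subject who leaves between the control and the Period 2 application is counted by one set of rules and left out by another.

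**Working it through.** **Inputs (section 4):** three sequences of 4 subjects; each subject has one control period and two active periods.

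**Plan's own figure:** 3 × 4 = 12 subjects, as stated. This gives 12 × 1 = 12 control periods and 12 × 2 = 24 active periods.

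**Position of the control against the first product application**

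| Sequence | n | Period of first application | Period of control | Control-period AEs under literal 7.4 |
|---|---|---|---|---|
| 1 | 4 | 1 | 3 | treatment-emergent |
| 2 | 4 | 1 | 2 | treatment-emergent |
| 3 | 4 | 2 | 1 | screening event or medical history |

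- Control periods before any application: 4/12 = 33%.
- Control periods after an application: 8/12 = 67%.
- Active periods outside the treatment-emergent window: 0/24.

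Suppose that events are equally likely in every control period and that the summary is restricted to treatment-emergent events. Both are assumptions: 8.2 says only that AEs are summarised descriptively. The expected control count is then 8/12, or two thirds, of its full value, while the active count is complete.

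**A Sequence 3 subject who leaves after the control and before the Period 2 application**

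| Section | Literal result |
|---|---|
| 5.1 | not a drop-out, not in the database, may be replaced by a standby |
| 10.6 | outside the set for whom a CRF is required |
| 7.4 | AEs during the study go to the CRF |
| 8.2 | in the safety population |
| 9.1 | in the PK analysis, if sampled enough |

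These five results cannot all be followed. The number of such subjects can be anything from 0 to 4. That is only the logical range, because the protocol gives no withdrawal rate.

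**After one anchor at the first study treatment:** 12/12 control periods and 24/24 active periods lie in the treatment-emergent window, and the database and CRF rules agree with 8.2 and 9.1.

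**The case against.** The best answer is that the protocol does not use its dosing terms literally. Table 1 marks a drug application on Days 1, 8 and 15 for all subjects, whatever the sequence, and its footnote b equates inclusion with the first drug administration. Sections 4, 6.1.2 and 6.2.1 use drug application or drug administration for every period. Appendix 1 suggests that the authors treated drug application and treatment as the same thing when the control was added. On that usage the first dose is Day 1 for everyone. Section 7.4 then causes no difficulty, and 5.1 and 10.6 can arguably be read the same way.

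Much of this stands: a Day 1 start is probably what was meant. But no section defines it, and section 6.1.2.1 says in terms that the control has no application. The wording of 5.1 and 10.6, which refers to the investigational product itself, fits the loose usage least well.

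A second answer is that section 7.1 defines an AE as an occurrence in someone who has been given an investigational product. Withholding the treatment-emergent label before any exposure is consistent with that. This is fair, and it means that changing 7.4 alone would create a new mismatch. It does not explain why 8.2 counts the same subjects as treated.

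A third answer is that the SAP, which is not shown, may set the treatment-emergent window. It may, but who enters the database and for whom a CRF is completed are protocol rules that already conflict with 8.2.

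**Conclusion.** The point holds as a minor inconsistency. On a literal reading, 4 of 12 control periods fall outside the treatment-emergent window while 8 of 12 control periods and all 24 active periods fall inside it. One narrow type of early leaver is also in the safety population but not in the database or CRF set. The first effect depends on taking the dosing terms literally; the second also needs a Sequence 3 withdrawal between the Period 1 control and the Period 2 application.

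A reader might infer more: that control-period AEs would be lost, or that the PK result is compromised. The documents do not support either.
- Section 7.4 says that all AEs during the study "will be recorded for all subjects and reported in the CRF", so the events are captured and only their label is in doubt.
- Section 9.1 still requires the control-period samples to be assayed and included.
- Baseline adjustment in section 9.2 is done within each subject and period, so active-period parameters do not depend on this wording.
- Safety is the secondary objective and is summarised descriptively, and section 9.3 plans no statistical analysis, so no test is affected.

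**What to change.** Use one anchor, *start of the first study treatment (Treatment-1, -2 or -3)*:

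1. **7.4:** put it in place of both the first-dose and the study-medication wording.
2. **10.6:** define an included subject as one who has started at least one study treatment, control included.
3. **5.1:** split the sentence and move only the database clause to the new anchor. The same sentence also decides who is a drop-out, and 5.1 goes on to say "Drop-outs will not be replaced", so moving the whole sentence would change the replacement rule without anyone having decided to. Leave that rule to the sponsor, but state the disposition of a subject who leaves after the control only.
4. **7.1:** extend the AE definition so that events in a control period qualify.
5. **8.2:** summarise AEs by the treatment period in which they start, with a denominator for each treatment.

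The cost is a few wording changes, with no new data, visits or staff. The one drawback is that if a control-only leaver is replaced, the safety population can exceed 12. Denominators per treatment deal with that in the tables.

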7.5. SERIOUS ADVERSE EVENT REPORTING REQUIREMENTS

The clinical site will notify any SAE to the sponsor, without regard to causality, within 24 hours after becoming aware of its occurrence. This notification will contain a description of the observed symptoms and an assessment of causality. A detailed report will be sent in the following days.

The notification, in English, should be directed to the following sponsor representative:

[name], Clinical Research Associate II Medline Industries, Inc. [contact] (Working hours) [contact] (nights, weekends, and holidays) [contact]

Email:[contact]

A SAE will be considered as "unexpected" when the nature or severity is not consistent with information in the relevant source document(s).

Algorithme Pharma will determine whether any serious unexpected related adverse event must be reported to the IRB. If so, the event will be reported via fax or email within 15 calendar days of the investigator or staff becoming aware of the event.

The sponsor will be responsible for notifying FDA and all participating investigators of any SAE observed during conduct of the study, regardless of whether the event is considered drug related, as soon as possible but in no case later than 15 calendar days after becoming aware of its occurrence. If the adverse event is fatal or life-threatening, the sponsor must also notify the Clinical Safety Coordinator in CDER's Office of Generic Drugs as soon as possible but in no case later than 7 calendar days after becoming aware of its occurrence.

7.6. PREGNANCY

Pregnancy in a female subject in the study shall be reported to the sponsor within 24 hours of the knowledge of its occurrence by the clinical site (for pregnancies occurring during the course of the study or immediately following the end of the study). Because of the possibility that the fetus/embryo could have been exposed to the study drug through the parent and for the subject's safety, the pregnancy will be followed up to determine its outcome, including spontaneous or voluntary termination, details of birth, presence or absence of any birth defects, congenital anomalies, or maternal and/or newborn complications.

The pregnancy will be recorded and reported by the clinical site to the sponsor. Pregnancy follow-up will also be properly recorded to ensure quality and completeness of the data belonging to the study drug and will include an assessment of the possible causal relation between the study drug and any pregnancy outcome. Any SAE experienced during pregnancy will be reported on a SAE Report Form.

8. METHODS OF EVALUATION

8.1. DRUG CONCENTRATIONS

8.1.1. Bioanalytical assays

Chlorhexidine plasma concentrations will be measured according to a validated bioanalytical method.

The validated range can be truncated when less than 5 calibration standards appear to be below the expected C_{max} , provided that this new calibration curve range is validated prior to use.

In the event that the study is conducted in multiple groups, sample analysis will begin only after completion of the clinical portion of the last group (i.e. after the last sample is collected).

Where possible, all samples from each subject will be analyzed on the same standard curve. Quality control samples will be distributed through each batch of study samples assayed. Samples with drug concentrations greater than the upper limit of quantification (ULQ) of the assay range will be diluted with the appropriate drug-free biological fluid and re-assayed; those which are below the lower limit of this range will be reported as being below limit of quantitation concentrations (BLQ). The analysts will not have access to the randomization scheme.

8.1.2. Aberrant values and retested samples

Unacceptable values attributable to bioanalytical reasons will be determined by the bioanalytical facility. Such re-assayed samples will be termed "repeats". All cases of re-assay will be reported in the final report.

No samples will be repeated for pharmacokinetic reasons.

